4.4.4 Prohibited Medication Use Prior to Peak Expiratory Flow Rate and Spirometry Measurements

Patients will measure PEFR prior to taking their asthma controller medications (see Section 4.5.8.2 for details). At specified timepoints during the study, patients will undergo pre-bronchodilator spirometry measurements in the clinic (see Section 4.5.7 for details). Patients must comply with the following restrictions prior to PEFR and spirometry measurements:

- Twice-daily LABA and LAMA: prohibited within 12 hours prior to PEFR or spirometry
- Once-daily LABA and LAMA: prohibited within 24 hours prior to spirometry
- SABA or SAMA: prohibited within 4 hours prior to spirometry

If the patient has not complied with the above restrictions prior to spirometry measurements, their visit should be rescheduled (see Section 4.5.7), with the exception of an unscheduled visit.

4.5 STUDY ASSESSMENTS

The schedule of activities to be performed during the study is provided in [Appendix 1](#). All activities should be performed and documented for each patient.

Patients will be closely monitored for safety and tolerability throughout the study.

4.5.1 Informed Consent Forms and Screening Log

Written informed consent for participation in the study must be obtained before performing any study-related procedures (including screening evaluations). Informed Consent Forms for enrolled patients and for patients who are not subsequently enrolled will be maintained at the study site.

All screening evaluations must be completed and reviewed to confirm that patients meet all eligibility criteria before enrollment. The investigator will maintain a screening log to record details of all patients screened and to confirm eligibility or record reasons for screening failure, as applicable.

4.5.2 Medical History, Concomitant Medications, and Demographic Data

Medical history, including clinically significant diseases, surgeries, cancer history (including prior cancer therapies and procedures), reproductive status, smoking/vaping history, and use of alcohol and drugs of abuse, will be recorded at screening. In addition, all medications (e.g., prescription drugs, over-the-counter drugs, vaccines, herbal or homeopathic remedies, nutritional supplements) used by the patient 7 days prior to screening (for medications not intended for the treatment of asthma) or 3 months prior to screening (for medications intended for the treatment of asthma) will be recorded. At the time of each follow-up limited physical examination, an interval medical history should be obtained and any changes in medications and allergies should be recorded.

Demographic data will include age, sex, and self-reported race/ethnicity. Race/ethnicity is recorded because of the potential contribution of this variable to tryptase genetics, as well as differences in observed pharmacokinetics, pharmacodynamics, toxicity, and/or response to treatment.

4.5.3 Physical Examinations

A complete physical examination, performed at screening and other specified visits, should include an evaluation of the head, eyes, ears, nose, and throat, and the cardiovascular, dermatologic, musculoskeletal, respiratory, gastrointestinal, and

neurologic systems. Any abnormality identified at during the screening period should be recorded on the General Medical History and Baseline Conditions eCRF.

Limited, symptom-directed physical examinations and examination for infusion-related reactions should be performed at specified visits during the placebo-controlled period and as clinically indicated. Changes from baseline abnormalities should be recorded in patient notes. New or worsened clinically significant abnormalities should be recorded as adverse events on the Adverse Event eCRF.

4.5.4 Vital Signs

Vital signs will include measurements of respiratory rate, pulse rate, and systolic and diastolic blood pressure while the patient is in a seated position (resting for at least 5 minutes), and temperature. Record abnormalities observed at baseline on the General Medical History and Baseline Conditions eCRF. At subsequent visits, record new or worsened clinically significant abnormalities on the Adverse Event eCRF.

4.5.5 Nasosorption

Nasosorption is a minimally invasive technique that samples the nasal mucosal lining fluid using the Nasosorption™ FX•i device (Hunt Developments), which has been used in humans. The aseptic device is inserted into the nostril with the absorbent strip held flat against the surface of the inferior turbinate for 60 seconds as described in the study pulmonary function testing (PFT) manual.

4.5.6 Fractional Exhaled Nitric Oxide

FeNO is a volatile marker of airway inflammation that decreases with ICS treatment. Standard nitric oxide machines (Circassia NIOX® VERO Nitric Oxide Monitor) will be provided to the site and should be used for all study-related FeNO measurements that will be performed in accordance with ATS published guidelines and described in the study PFT manual. Patients will be asked to refrain from nitrate-rich foods (such as processed meats [bacon, lunchmeat, hot dogs, sausage], spinach, green beans, broccoli, and cauliflower) for at least 8 hours prior to the study visit and to avoid food or drink for at least 1 hour prior to completing FeNO measurements. Patients must complete at least three (and up to six) separate measurements to obtain at least two nitric oxide plateau values that agree within 10% of each other according to ATS guidelines (training and guidance to be provided separately) (ATS 2005; Dweik et al. 2011).

4.5.7 Spirometry

Spirometry, including the procedure for bronchodilator testing, will be conducted as per the study PFT manual, which is based on the ATS/ERS Consensus Statement "Standardisation of Spirometry" (Miller et al. 2005). The manual will include information on equipment, procedures, patient instructions, and precautions. Standardized ATS- and ERS-compliant spirometric equipment (6600 VITALOGRAPH COMPACT™), including

software, will be dispensed to all sites. Training on equipment use, system calibration, and data storage and transfer will be provided.

Spirometric assessments will include FEV₁, FVC, percentage of predicted values for FEV₁ and FVC, FEV₁ to FVC ratio, and average forced expiratory flow during the middle portion of the expiration (FEF₂₅₋₇₅). The percentage of predicted values for FEV₁ and FVC will be derived from the third National and Nutrition Examinations Survey (Hankinson et al. 1999). Each test procedure requires that three valid spirometry maneuvers be performed within 1 hour. For safety reasons, consideration should be given to omitting spirometry if a patient is having an acute asthma exacerbation event at the time of the scheduled study visit. The acceptability of the data, including graphic representations of the maneuvers, will be determined by blinded over-readers. Calculation for the reproducibility of the acceptable maneuvers will be programmed.

Pre-bronchodilator spirometry evaluations should be performed before use of bronchodilators. Asthma therapies that may affect spirometry must be withheld until pre-bronchodilator spirometry measurements are completed. Patients must be made aware that bronchodilator use is prohibited within a specified window prior to each clinic visit, with the exception of an unscheduled visit, as detailed in Section 4.4.4. With the exception of an unscheduled visit, a patient's pre-bronchodilator spirometry testing must thus be rescheduled if the patient arrives for a scheduled study visit having used a bronchodilator within this restricted time window. To accommodate the rescheduled visit, the usual visit window specified in the schedule of activities (see [Appendix 1](#)) may be extended to ± 4 days for Week 2, ± 5 days for Week 3, and ± 6 days for all other visits.

Post-bronchodilator spirometry will be performed at screening. During this assessment, up to 8 puffs of SABA or nebulized equivalent (e.g., 2 treatments with 2.5 mg albuterol/salbutamol) will be administered in a step-wise fashion per ATS/ERS guidelines (Miller et al. 2005).

4.5.8 Assessments Completed by the Patient at Home

At the initial screening visit, patients will receive an eDiary and a peak flow meter to measure PEFR. Patients will be instructed in eDiary use and asked to use the eDiary twice per day (morning/evening) to record asthma-related symptoms, PEFR, and use of short-acting rescue therapy. The eDiary will remind patients twice daily to complete their entries and will provide a time window during which the entry must be completed at approximately the same time each day. Patients will use the eDiary during screening and through Week 50.

Compliance with the required use of the eDiary and PEFR measurements (see Section 4.1.1.1) must be demonstrated on 5 of 7 days during each of 2 consecutive weeks during the screening period and also during the 2 week run-in period. eDiary compliance less than 70% (fewer than 5 out of 7 days/week) during the screening period

will result in screen failure. eDiary compliance less than 70% (fewer than 5 out of 7 days/week) during the run-in period will result in study discontinuation. Site staff will review daily diary compliance at each subsequent visit and provide refresher training if compliance is consistently less than 70% between study visits.

4.5.8.1 Daily Diary Symptom-Related Asthma Assessments

The daily diary (see [Appendix 4](#) and [Appendix 5](#)) comprises:

- Daytime/nighttime asthma symptoms
- Nighttime awakenings
- Number of doses of short-acting rescue therapy

4.5.8.2 Peak Expiratory Flow Rate

PEFR measurements should consist of three good efforts. Patients should complete their PEFR measure prior to taking their daily LABA and LAMA asthma controller medication as prescribed. Patients will be given instructions on how to measure PEFR and record information in the eDiary.

On the days of study visits, if the patient has not performed the morning PEFR measurement before arrival at the clinic, the PEFR should be measured at the clinic.

4.5.9 Laboratory, Biomarker, and Other Biological Samples

Samples for the following laboratory tests will be sent to the study's central laboratory for analysis or analyzed at point of care, except where noted for pregnancy tests:

- Pregnancy tests
 - All women of childbearing potential will have serum pregnancy tests at central lab at screening. Urine pregnancy tests will be performed at sites' local lab or clinic prior to each administration of study drug, and at other specified visits after treatment discontinuation. Serum pregnancy tests will be confirmed at central labs and performed at subsequent visits if a urine pregnancy test is positive. Study drug will not be administered if a patient has a positive pregnancy test.
- Hematology: WBC count, RBC count, hemoglobin, hematocrit, platelet count, and differential count (neutrophils, eosinophils, basophils, monocytes, lymphocytes, other cells)
- Chemistry panel (serum or plasma): sodium, potassium, chloride, bicarbonate or total carbon dioxide (if considered standard of care for the region), glucose, BUN or urea, creatinine, calcium, magnesium, phosphate, total protein, albumin, total and direct bilirubin, ALP, ALT, AST, urate, LDH, creatine kinase, and HbA_{1c}
- HIV serology: HIV-1/2 antibody
- HBV serology: HBsAg, total HBcAb, and (if HBsAg test is negative and total HBcAb test is positive) HBV DNA

If a patient has a negative HBsAg test and a positive total HBcAb test at screening, an HBV DNA test must also be performed to determine if the patient has an HBV infection.

- HCV serology: HCV antibody and (if HCV antibody test is positive) HCV RNA
 - If a patient has a positive HCV antibody test at screening, an HCV RNA test must also be performed to determine if the patient has an HCV infection.
- TB: QFT-G test or PPD test
- Urinalysis includes dipstick (pH, specific gravity, glucose, protein, ketones, bilirubin, nitrite, blood) and microscopic examination (sediment, RBCs, WBCs, casts, crystals, epithelial cells, bacteria). If urinalysis is abnormal, reflex testing for culture and antibiotic sensitivity should be performed per local standard of care, if clinically indicated.
- Urine drug screen, including, but not limited to, amphetamines, barbiturates, benzodiazepines, cocaine, cotinine, marijuana/cannabinoids (tetrahydrocannabinol), methadone, methamphetamines, methylenedioxymethamphetamine, opiates, and phencyclidine

The following samples will be sent to one or several central laboratories or to the Sponsor or a designee for analysis:

- Serum samples for PK analysis
- Serum samples for immunogenicity analysis
- Serum, blood, urine, and nasal mucosal lining fluid samples for exploratory research on biomarkers

Exploratory biomarker research may include, but will not be limited to, active tryptase, total tryptase, urea, and inflammatory lipids. Research may involve extraction of DNA and genomic profiling through use of single nucleotide polymorphism analyses and next-generation sequencing (NGS) of a comprehensive panel of genes. Genomic research will be aimed at exploring inherited characteristics. NGS methods may include whole genome sequencing (WGS), but only at participating sites (see Section 4.5.13).

For sampling procedures, storage conditions, and shipment instructions, see the laboratory manual.

Unless the patient gives specific consent for his or her leftover samples to be stored for optional exploratory research (see Section 4.5.15), biological samples will be destroyed when the final Clinical Study Report has been completed, with the following exceptions:

- Serum samples collected for PK or immunogenicity analysis may be needed for additional immunogenicity characterization and for PK or immunogenicity assay development and validation; therefore, these samples will be destroyed no later than 5 years after the final Clinical Study Report has been completed.

- Serum, urine, blood, and nasal mucosal lining fluid samples collected for biomarker research will be destroyed no later than 5 years after the final Clinical Study Report has been completed.

When a patient withdraws from the study, samples collected prior to the date of withdrawal may still be analyzed, unless the patient specifically requests that the samples be destroyed or local laws require destruction of the samples. However, if samples have been tested prior to withdrawal, results from those tests will remain as part of the overall research data.

Data arising from sample analysis will be subject to the confidentiality standards described in Section [8.4](#).

Given the complexity and exploratory nature of exploratory biomarker analyses, data derived from these analyses will generally not be provided to study investigators or patients unless required by law. The aggregate results of any conducted research will be available in accordance with the effective Sponsor policy on study data publication.

4.5.10 [Electrocardiograms](#)

Single ECG recordings will be obtained at specified timepoints as outlined in the schedule of activities (see [Appendix 1](#)), and may be obtained at unscheduled timepoints as indicated.

All ECG recordings must be performed using a standard high-quality, high-fidelity digital electrocardiograph machine equipped with computer-based interval measurements. Lead placement should be as consistent as possible. ECG recordings must be performed after the patient has been resting in a supine position for at least 10 minutes. ECGs should not be obtained within 3 hours after any meal. Circumstances that may induce changes in heart rate, including environmental distractions (e.g., television, radio, conversation) should be avoided during the pre-ECG resting period and during ECG recording.

For safety monitoring purposes, the investigator must review, sign, and date all ECG tracings. Paper copies of ECG tracings will be kept as part of the patient's permanent study file at the site. Digital recordings will be stored at the study sites. The following should be recorded in the appropriate eCRF: heart rate, RR interval, QRS interval, PR duration, uncorrected QT interval, and QTcF based on the machine readings of the individual ECG tracings. Any morphologic waveform changes or other ECG abnormalities must be documented on the eCRF. If considered appropriate by the Sponsor, ECGs may be analyzed retrospectively at a central laboratory.

If at a particular postdose timepoint the QTcF is >500 ms and >60 ms longer than the baseline value, another ECG must be recorded, ideally within the next 5 minutes, and ECG monitoring should continue until QTcF has stabilized on two successive ECGs.

The Medical Monitor should be notified. Standard-of-care treatment may be instituted per the discretion of the investigator. If a PK sample is not scheduled for that timepoint, an unscheduled PK sample should be obtained. A decision on study drug discontinuation should be made, as described in Section 5.1.2.3. The investigator should also evaluate the patient for potential concurrent risk factors (e.g., electrolyte abnormalities, co-medications known to prolong the QT interval, severe bradycardia).

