5.1.2.3 Management of Increases in QT Interval

Study drug should be discontinued in patients who develop any of the following, unless there is a clear alternative cause for the changes:

- Sustained absolute (at least two ECG measurements >30 minutes apart) QTcF that is >500 ms or >60 ms longer than the baseline value
- An episode of torsades de pointes or a new ECG finding of clinical concern

Of note, if there is a new intraventricular conduction block, the increase in QRS complex duration should be subtracted from the QTcF change, because this represents an increase in QTcF unrelated to alterations in repolarization. Also of note, it is not uncommon to record arrhythmias such as non-sustained ventricular tachycardia, supraventricular tachycardia, pauses, or atrial fibrillation in healthy volunteers receiving placebo during periods of extended ECG monitoring. Therefore, it is critical that expert cardiology advice be sought to confirm any ECG changes and to ascertain the likelihood

of a drug-induced arrhythmia versus the background occurrence of this arrhythmia. In such a situation, saving all available ECG data is highly suggested.

Management of patients with sustained QTcF prolongation should include close monitoring, with ECGs repeated at least hourly until two successive ECGs show resolution of the findings, correction of any electrolyte abnormalities, and possible discontinuation of other concomitant medications that are known to prolong the QT interval. Consultation with a cardiologist or electrophysiologist is recommended to help in the management of such patients. The Medical Monitor should be notified as soon as possible. In more complicated or severe occurrences, hospitalization should be considered.

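### The mandatory repeat ECG in Section 4.5.10 requires both QTcF limits to be exceeded, while the stopping rule it feeds in Section 5.1.2.3 applies on either one

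*Protocol*

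**What the plan says.** Section 4.5.10 (Electrocardiograms) sets the ECG regimen. "Single ECG recordings will be obtained at specified timepoints", and further tracings "may be obtained at unscheduled timepoints as indicated". The investigator must review and sign every tracing. The mandatory response to a long QTcF reads: "If at a particular postdose timepoint the QTcF is >500 ms and >60 ms longer than the baseline value, another ECG must be recorded". The repeat is ideally taken within 5 minutes, and "ECG monitoring should continue until QTcF has stabilized on two successive ECGs". The same paragraph adds Medical Monitor notification, an unscheduled PK sample if none is due, and an evaluation of concurrent risk factors. It closes the loop with: "A decision on study drug discontinuation should be made, as described in Section 5.1.2.3".

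Section 5.1.2.3 says study drug should be discontinued, absent a clear alternative cause, for either of two findings. The first is prolongation described as "Sustained absolute (at least two ECG measurements >30 minutes apart") with "QTcF that is >500 ms or >60 ms longer than the baseline value". The second is torsades de pointes or a new ECG finding of clinical concern. For patients whose prolongation is already sustained, the section asks for ECGs at least hourly and says "The Medical Monitor should be notified as soon as possible".

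**The concern.** The two sections use the same two limits with opposite connectives, and one refers to the other. The mandatory trigger is therefore narrower than the rule it is meant to inform.

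This matters because the sustained-prolongation rule cannot be applied to a single tracing, and a single tracing is all that a scheduled visit provides. After a reading over one limit only, the second ECG, the unscheduled PK sample and the risk-factor evaluation all become optional. The hourly ECGs in Section 5.1.2.3 do not fill the gap, because they begin once prolongation is known to be sustained, which is what the missing ECG would establish.

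The issue is patient safety: whether someone who may meet the protocol's own stopping criterion is dosed again without the check that would show it. No endpoint or efficacy analysis is affected.

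**Working it through.** **Inputs.** The two rules come from Sections 4.5.10 and 5.1.2.3. The QTcF entry limits (450 ms for men, 470 ms for women) come from Section 4.1.2. Dosing weeks (2, 6, then every 4 weeks through 46) come from Section 3.1. ECG visits come from Appendix 1. The plan states no figure on this point to reproduce.

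**The two rules.** Let B be baseline QTcF and Q a post-dose reading, both in whole ms.

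- Mandatory repeat (both limits): Q > 500 and Q − B > 60, that is, Q ≥ max(501, B + 61).
- Stopping threshold (either limit): Q > 500 or Q − B > 60, that is, Q ≥ min(501, B + 61).
- Uncovered width: max − min = |501 − (B + 61)| = |B − 440|.

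| Baseline B (ms) | Stopping threshold from | Mandatory repeat from | Uncovered readings | Width (ms) |
|---|---|---|---|---|
| 400 | 461 | 501 | 461–500 | 40 |
| 420 | 481 | 501 | 481–500 | 20 |
| 440 | 501 | 501 | none | 0 |
| 450 (male entry limit) | 501 | 511 | 501–510 | 10 |
| 465 | 501 | 526 | 501–525 | 25 |
| 470 (female entry limit) | 501 | 531 | 501–530 | 30 |

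Two examples:

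- B = 420, Q = 485: the change is 65 ms, over 60, but 485 does not exceed 500.
- A woman with B = 465, Q = 510: 510 exceeds 500, but the change is 45 ms.

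Both readings cross the stopping threshold, and neither triggers a mandatory repeat.

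**Time to the next scheduled tracing.** Counted by column, the ECG row of Appendix 1 gives screening, randomization, Weeks 3, 30, 50 and 54, plus unscheduled and early-termination visits. As a check, the second mark in the methacholine row falls in the same column as the Week 30 ECG, which agrees with the Week 30 test in Section 4.5.14.

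- Week 3 to Week 30: 30 − 3 = 27 weeks. Doses at Weeks 6, 10, 14, 18, 22 and 26, so six.
- Week 30 to Week 50: 50 − 30 = 20 weeks. Appendix 1 places assessments before dosing, so the Week 30 dose follows that ECG. Doses at Weeks 30, 34, 38, 42 and 46, so five.

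**When the trigger does fire.** A repeat within about 5 minutes, then monitoring until two successive ECGs are stable, can finish inside 30 minutes. The mandated tracings need not include one more than 30 minutes after the first, which Section 5.1.2.3 needs.

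**Consistency with the SAP.** Output 4.26 tabulates QTcF above 500 msec and change above 60 msec as separate categories. Section 5.1.2.3 likewise gives each limit weight on its own. The *and* in Section 4.5.10 is the exception, and no reason is given for it.

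**The case against.** The strongest reply is that the sections serve different purposes. Section 4.5.10 sets an urgent response, for which a stricter trigger is defensible, while Section 5.1.2.3 stands alone as a stopping rule and does not need the trigger to fire.

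There are also other safeguards. Its second criterion, a new ECG finding of clinical concern, permits stopping on the first tracing. The section urges cardiology advice on ECG changes. The investigator signs every tracing and may order another. Section 4.6.1 requires discontinuation for any condition judged to jeopardize safety, and Section 5.1.1.2 requires clinical stability before each dose. On this view, six further doses is a stacked worst case.

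It can be added that the dose count rests on reading columns in a poorly extracted table, where the FeNO row read the same way shows no Week 50 mark although Week 50 FeNO is a secondary endpoint. Section 5.1.1 identifies no important mechanism-based risk, and enrollment is permanently halted.

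Much of this stands as context. Many investigators would repeat the ECG, the six-dose case needs several lapses together, and the change reaches only remaining visits. However, each safeguard named depends on judgment, and none makes the confirmatory tracing mandatory. The ECG row itself reads as complete and agrees with the methacholine row.

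**Conclusion.** The concern holds and should be corrected. The gap is in what is required, not in what is allowed: a reading over one limit crosses the stopping threshold, yet no text orders the second ECG needed to apply it. The band is |baseline − 440| ms wide, 10 to 40 ms across the non-zero baselines shown, and disappears only at 440 ms. Up to six doses (after Week 3) or five (from Week 30) can fall before the next scheduled tracing.

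These results assume whole-millisecond readings, illustrative baselines within the entry limits, and the Appendix 1 ECG row as read by column. The documents give no distribution of baseline QTcF, no frequency of one-limit readings and no QT signal, so the figures describe bands and intervals and do not estimate risk.

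**What to change.** In Section 4.5.10, change *and* to *or*, so that a repeat ECG is mandatory when QTcF exceeds 500 ms or is more than 60 ms above baseline. Keep the immediate repeat and the monitoring until stable. Add that at least one further ECG be recorded more than 30 minutes after the first, so that the sustained criterion can be assessed. Section 5.1.2.3 needs no change. On a single reading, the trigger and the stopping threshold then coincide at every baseline.

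The cost is a wording change in one paragraph, a few more repeat ECGs, occasional unscheduled PK samples, and at least 30 more minutes at the visit for affected patients. With enrollment halted, it applies only to the remaining visits of patients already enrolled.
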